6 TRIAL DESIGN AND PROCEDURES

6.1 Trial Design

The trial will comprise 2 parts:

Part 1: The first 3 patients selected for the study will be treated with active drug in open-label manner. They will have weekly clinic visits for up the first 2 weeks and thereafter biweekly visits. When the third of the first 3 patients has completed their first 2 weeks treatment, the PI will review the safety, tolerability and ease of application for each patient before deciding to proceed to the randomised, double masked comparative phase of the study (Part 2). The 3 patients will continue on the study and complete the 8 weeks trial as open label patients.

Part 2: A randomised, double-masked, placebo controlled trial of topical rVA576 or placebo eye drops in moderate to severe AKC, VKC and severe allergic conjunctivitis (SAC or PAC). The part 2 trial population will comprise 16 patients who meet all the inclusion and none of the exclusion criteria (Section 4.1 and Section 4.2).

6.2 **Duration of trial**

The estimated duration of the study for an individual patient is approximately 13 weeks. The duration from the First Patient Screened to Last Patient Last Visit (LPLV) will be approximately 7-8 months.

At the end of the 56 Days the subjects will return to their usual standard of care therapy, as this is the first clinical trial of rVA576 in patients with AKC, VKC and severe allergic conjunctivitis (SAC or PAC) and the long-term efficacy and safety is not yet established.

Figure 6 Trial Design

TRACKER Trial Design

Protocol AK701 - version 8.0 10 February 2020 © Akari Therapeutics Plc

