11 STATISTICS

11.1 Statistical Methods

A Statistical Analysis Plan (SAP) will be prepared and finalised prior to unmasking of the study for the analysis. The SAP will provide full details of the analyses, data displays, algorithms to be used for data derivations and handling of missing data. SAS[®] statistical software version 9.3 or above will be used for analysing the data (SAS Institute, Inc., Cary, North Carolina).

Continuous variables will be summarized using the number of patients, number of missing values, mean, median, standard deviation, standard error, minimum, and maximum. Categorical variables will be summarized using number of patients, number of missing values, frequency counts, and percentages. Unless otherwise specified, missing data will not be included in the denominator for percentage calculation. Change from baseline may be substituted with percentage change from baseline or ratio to baseline if the distribution of an individual parameter suggests this.

The baseline value will be defined as the pre-dose value on Day 1, if that is missing, it will be defined from the most recent value available.

The two parts of the study will be reported separately. Data from patients included in Part 1 will only be listed, while the following sections apply for data from patients included in Part 2.

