2.2 Study Endpoints

The primary endpoint of the study is:

• Incidence of ocular treatment emergent adverse events during the treatment period. The adverse events (AEs) which have occurred during the 56 days following randomisation (Part 2 of the study only) will be considered in the analysis of the primary safety outcome.

The secondary endpoints are:

- Post-instillation comfort, as graded on patient diary cards at the following intervals: Days 1 to 14, 15 to 28, 29 to 42 and 43 to 56
- Visual acuity by Early Treatment Diabetic Retinopathy Study (ETDRS) charts comparison from Day 1 to Day 56
- Change from Day 1 in composite clinical scores (including Symptom and Sign subcomponents) at Day 14, 28, 42 and 56

- Number and percentage of patients with Matrix metalloprotease 9 (MMP-9) < 40 ng/mL and ≥ 40 ng/mL assessed using Inflamma Dry (Quidel) device at Days 1, 28 and 56
- Change from Day 1 in Tear film break up time (TBUT) at Day 14, 28, 42 and 56

The exploratory endpoints are:

- Systemic absorption by blood sampling
- If enough tear fluid can be collected analysis of complement C3, C5 and leukotriene B4 (LTB4) will be performed
- A comparison of the number of patients requiring rescue therapy at any stage of the trial and the number on such therapy at the end of the trial

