3 SAMPLE SIZE

Up to 19 patients, 3 active in Part 1 of the study and up to 16 randomised to active or placebo in Part 2, will be enrolled under this protocol. The sample size for this study was determined based on practical, and not statistical, considerations.

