4 RANDOMISATION

Patients will only be randomised in Part 2 of the study. They will be randomised in a 1:1 fashion. There will be no stratification.

5 INTERIM ANALYSIS & REPORTING OF PART 1

No interim analysis is planned.

The decision to proceed to Part 2 will be determined through PI and an independent clinician review of the data for the first three patients up until the time that the third patient has completed the second week of the study. Medical History, Adverse Event, Concomitant Medication and Compliance data will be reviewed via the clinical database. A trend analysis will be carried out for the adverse events. No statistical outputs will be produced at this time, but the patients from Part 1 will be included in the same patient listings as for Part 2 as a separate group. Should the study be discontinued after Part 1, the listings described in the sections below will be produced for Part 1 only. The summary tables and figures described in the following sections relate to Part 2 only unless otherwise stated.

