6.14 Safety Evaluation

6.14.1 Adverse Events

AEs will be coded using the latest MedDRA dictionary version. The version used will be indicated in the data summaries and listings.

Ocular AEs will be identified using SOC "Eye disorders".

A treatment-emergent adverse event (TEAE) is defined as an AE that started on or after the start of the administration of study treatment. If AE dates are incomplete and it is not clear whether the AE was treatment-emergent, it will be assumed to be treatment-emergent. When the AE occurs on the same day as start of administration of study treatment a separate file will be transferred from data management to indicate whether they are treatment emergent or not (see Data Management Plan section 6).

If it is not confirmed via Data Management, the start date will be imputed as the date of the first dose of study drug. AEs will be considered treatment-emergent if all or part of the date of onset of the AE is missing and it cannot be determined if the AE meets the definition for treatment-emergent.

Any AE commencing after the last administration of study treatment (Day 56) plus 30 days will not be considered treatment emergent.

A treatment-related TEAE is defined as a TEAE that is possibly related or related to the study treatment. If the TEAE has a missing relationship it is assumed to be related to the study treatment for analysis purposes.

6.14.1.1 **Primary Endpoint**

The number and percentage of patients who experienced ocular TEAEs will be presented for each treatment group. Treatment groups will be presented in the following order: "Part 1, Treatment: nomacopan 0.25% eye drops", "Part 2, Treatment: nomacopan 0.25% eye drops", "Part 2, Treatment: Placebo".

The difference in the percentage of patients (nomacopan -placebo) and exact 95% confidence interval for the difference, using Chan and Zhang method (1999), will be presented for those in part 2 of the study (nomacopan-placebo) and for those in both parts of the study combined (nomacopan-placebo).

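### SAP 6.14.1.1 adds to the randomised Part 2 result an unlabelled pooled contrast in which three open-label Part 1 patients join the active side only

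*SAP*

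**What the plan says.** SAP 6.14.1.1, headed Primary Endpoint, plans the nomacopan-minus-placebo difference in the percentage of patients with ocular TEAEs, with an "exact 95% confidence interval for the difference, using Chan and Zhang method (1999"). The first such contrast "will be presented for those in part 2 of the study (nomacopan-placebo"). The second is "for those in both parts of the study combined (nomacopan-placebo"). The section does not say which of the two is primary, or that either is supportive.

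Other places describe the population differently:

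- Protocol 11.1 has the two parts reported separately: "Data from patients included in Part 1 will only be listed".
- Protocol 5.2.1 and SAP 2.2 define the primary outcome on events in the 56 days after randomisation, and SAP 2.2 adds: "Part 2 of the study only) will be considered in the analysis of the primary safety outcome".
- SAP 5 confines summary tables to Part 2 by default but allows stated exceptions.
- SAP 6.17 declares that the Safety Analysis Set now takes in all treated patients from both parts. It does not mention a pooled between-arm contrast.

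On who the Part 1 patients are, Protocol 6.1 says: "The first 3 patients selected for the study will be treated with active drug in open-label manner". SAP 4 says: "Patients will only be randomised in Part 2 of the study. They will be randomised in a 1:1 fashion. There will be no stratification".

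**The concern.** Every Part 1 patient receives active drug, so combining the parts adds patients to one side only. The added patients differ from the randomised ones in ways that bear on an adverse-event count:

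- They know they are on active drug, and some ocular events are reported by the patient.
- They have an extra Day 7 visit at which adverse events are collected (Protocol 17.3, patients 1 to 3 only).
- They are seen by the PI, whereas Part 2 patients are seen by a masked observer (Protocol 6.7).
- They are the first three enrolled and have no concurrent placebo group.

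The primary endpoint's time window also cannot be applied to them as written, because it runs from randomisation and they are never randomised.

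At stake is the reading of the main safety result. Two differences and two intervals would stand under one Primary Endpoint heading. They may disagree, and nothing tells the reader that only one rests on randomisation and masking.

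**Working it through.** **Inputs.** Patient numbers come from SAP 3: "Up to 19 patients, 3 active in Part 1 of the study and up to 16 randomised to active or placebo in Part 2". Allocation in Part 2 is 1:1 (SAP 4). The 8 v 8 split is an assumption: full enrolment and exact balance. The documents give no ocular TEAE rate, so every event count and rate below is also an assumption.

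**The plan's own figure.** 3 + 16 = 19, which agrees with the stated maximum. The documents give no power or interval width to reproduce; the sample size is declared to be practical.

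**Composition.** Pooled active arm: 8 + 3 = 11. Non-randomised share: 3/11 = 27.3%. Placebo arm: 8, none from Part 1.

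**Shift caused by pooling.** Let a and b be the Part 2 active and placebo counts, and k the Part 1 count.

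- Part 2 difference: a/8 - b/8
- Pooled difference: (a + k)/11 - b/8
- Pooled minus Part 2: (a + k)/11 - a/8 = 3/11 x (k/3 - a/8)

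The shift is therefore 3/11 of the gap between the Part 1 rate and the Part 2 active rate. A gap of 10 points gives 2.7 points, 30 gives 8.2 and 50 gives 13.6.

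**Assumed illustrations.** Differences are in percentage points. The intervals are Chan-Zhang exact 95%, from two inverted one-sided 2.5% tests on the score statistic, with the nuisance rate maximised on a grid and differences stepped by 0.5 point.

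| Part 2 counts | Part 2 only | Pooled, 0/3 in Part 1 | Pooled, 3/3 in Part 1 |
|---|---|---|---|
| 2/8 v 2/8 | 0.0 (-45.0 to 45.0) | -6.8 (-49.0 to 33.0) | +20.5 (-26.0 to 60.0) |
| 4/8 v 2/8 | +25.0 (-25.5 to 67.5) | +11.4 (-35.0 to 52.0) | +38.6 (-9.0 to 75.5) |
| 5/8 v 1/8 | +50.0 (-0.5 to 84.5) | +33.0 (-15.5 to 68.5) | +60.2 (12.0 to 87.5) |
| 7/8 v 2/8 | +62.5 (9.0 to 91.5) | +38.6 (-9.0 to 75.5) | +65.9 (18.5 to 91.5) |

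For the second row: 4/11 - 2/8 = 36.4% - 25.0% = +11.4, and 7/11 - 2/8 = 63.6% - 25.0% = +38.6.

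The sign can change. 5/8 - 4/8 = +12.5, but 5/11 - 4/8 = 45.5% - 50.0% = -4.5.

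Whether the interval excludes zero can change in both directions. In the last row, a difference present in the randomised data is lost with 0/3. In the row above it, one appears with 3/3.

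**How often the interval excludes zero when the two Part 2 arms have the same true rate** (full binomial enumeration):

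| Common Part 2 rate | Part 2 only | Pooled, Part 1 rate the same | Pooled, Part 1 rate 0.9 | Pooled, Part 1 rate 1.0 |
|---|---|---|---|---|
| 0.2 | 2.0% | 2.9% | 8.4% | 10.3% |
| 0.3 | 2.8% | 3.4% | 7.2% | 8.5% |
| 0.5 | 2.6% | 3.3% | 4.5% | 5.2% |

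The pooled interval stays below 5% when Part 1 and Part 2 share a rate. It goes above 5% only when the Part 1 rate is far higher.

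**The case against.** There is a fair defence of the combined contrast.

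- It is additional. The Part 2 difference and interval are kept and come first, and SAP 2.2 still ties the primary outcome to Part 2.
- SAP 6.14.1.1 already shows Part 1 nomacopan, Part 2 nomacopan and Part 2 placebo as three groups, so a reader can see what pooling changed and undo it.
- The primary safety objective covers both parts (Protocol 5.1, SAP 2.1), SAP 5 permits stated exceptions, and SAP 6.17 openly declares the wider safety set.
- The study is not powered for the primary analysis (Protocol 11.5), and no decision rule depends on either interval.
- The illustrative counts are assumed, 0/3 and 3/3 are extremes, and the shifts are small beside intervals that span roughly 75 to 100 points.

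All of this stands, and it limits the point. A reader might infer that the SAP breaks the randomised comparison. It does not: that comparison is intact and reported. A reader might also infer that the interval method is invalid without randomisation. That is not so either: Chan-Zhang is an interval for two binomial proportions, and randomisation bears on whether the difference can be read as a treatment effect.

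The defence does not cover the contrast itself. An objective or a safety set that includes Part 1 supports describing those patients. It does not require setting them against a placebo group from another part of the trial. The declaration in SAP 6.17 is about who is in the set, and it does not touch the listing-only rule or the added between-arm estimate. The three separate columns also mean that deleting the contrast loses no safety data.

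**Conclusion.** The point holds in a limited form. Under the primary endpoint heading, the SAP plans a between-arm estimate that is partly non-randomised and unmasked. It has no supportive label, runs against Protocol 11.1 and the Part 2-only outcome definition, and is missing from the SAP's own list of changes.

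Its size depends on quantities the documents do not give. With 8 v 8 in Part 2, the pooled figure moves by 3/11 of the gap between the Part 1 and Part 2 active rates, in either direction, and by nothing on average if those rates are equal. Open-label reporting, the extra visit and earlier enrolment make equality uncertain, but nothing in the documents shows which way the rates would differ.

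A reader might conclude that the primary result is biased or that the trial's safety conclusion is unsafe. The documents do not support that: the Part 2 interval is unaffected and is reported. The correction is worth making because it is cheap and removes a second, confounded figure that could be read as a primary result.

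**What to change.** In SAP 6.14.1.1, delete the combined-parts difference and its interval, and state that the Part 2 difference with its Chan-Zhang interval is the sole primary analysis. Keep the Part 1 column that the section already presents, as description with no contrast to placebo. Add a line to SAP 6.17 saying that Part 1 ocular TEAEs are tabulated descriptively, since Protocol 11.1 provides for listing only.

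If the sponsor wishes to retain the combined contrast, label it supportive and non-randomised in the text and in the table, state the time window used for Part 1 patients, and declare it in SAP 6.17 as a departure from the protocol.

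The cost of deletion is one SAP sentence removed, two short ones added and one fewer table row. No data collection changes, and no Part 1 safety information is lost.

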6.14.1.2 Other Summary Tables

A summary table will present the following for Part 1 and Part 2,:

- TEAEs (events and patients).
- Serious TEAEs (events and patients).
- Serious study treatment related TEAEs (events and patients).
- TEAEs by severity (mild/moderate/severe) (events and patients).
- TEAEs by relationship to study treatment and the pooled study treatment related category (events and patients).
- TEAEs leading to discontinuation of study treatment (patients only).
- Study treatment related TEAEs leading to discontinuation of study treatment (patients only).
- TEAEs leading to death (patients only).

In the above summaries, if a patient experienced more than one TEAE, the patient will be counted once using the most related event for the "by relationship to study treatment" and "related to study treatment" summaries and at the worst severity for the "by severity" summary.

The following tables will be presented:

- TEAEs by system Organ Class (SOC) and Preferred Term (PT).
- TEAEs by PT.
- TEAEs by SOC, PT and severity
- TEAEs by SOC, PT and relationship to study treatment and the pooled related categories (related).

For all of the above, SOC and PT will be presented in decreasing frequency of the total number of patients with TEAEs.

Further details of the above four tables are given below:

- 1. If a patient experienced more than one TEAE, the patient will be counted once for each SOC and once for each PT.
- 2. If a patient experienced more than one TEAE, the patient will be counted once for each PT.
- 3. If a patient experienced more than one TEAE, the patient will be counted once for each SOC and once for each PT at the worst severity.
- 4. If a patient experienced more than one TEAE, the patient will be counted once for each SOC and once for each PT using the most related event.

AE data will be listed in full and this will also include a treatment emergent flag, cessation of event relative to first dosing of study treatment and duration of AE. The listing will be reported by events during "Days 1-56" (treatment period) and "Days 57-84" (follow-up period).

This listing will be repeated presenting only serious TEAEs.

6.15 Pregnancy Test

All pregnancy test details will be listed.

6.16 Eye Swab

All eye swab data will be listed.

6.17 Changes from the Protocol Planned Analysis

- Section 11.1 of the protocol states that the baseline value will be defined as the pre-dose value on Day 1, if that is missing, it will be defined from the most recent value available. This has been updated to take account of any patients who do not take their first dose on Day 1.
- Section 11.3 of the protocol states that the weekly comfort scores for postinstillation comfort, as graded on patient diary cards will be compared. To be in-line with the secondary endpoint, the scores over the two-weekly period will be compared.
- Section 11.8 of the protocol states that the Safety Analysis Set will include only randomized subjects from Part 2 of the study. To be in line with ICH E9 guidelines section 6.3 we will include all treated subjects regardless of the part of the study they are enrolled into.

7 **REFERENCES**

